11.3 REPORTING TO HEALTH AUTHORITIES

Adverse event reporting to regulatory agencies will be done by the MAH according to local and international regulatory requirements.

12. PLANS FOR DISSEMINATING AND COMMUNICATING STUDY RESULTS

Results of this non-interventional study will be disclosed on external websites according to BI SOP. The rights of the investigator and of the sponsor with regard to publication of the results of this study are described in the investigator contract. As a general rule, no study results should be published prior to finalization of the study report.

ANNEX 1. LIST OF STAND-ALONE DOCUMENTS

Number	Document Reference Number	Date	Title
1	Not applicable	23 September 2016	PACT-Q1 - Taiwan/Mandarin
2	Not applicable	23 September 2016	PACT-Q2 - Taiwan/Mandarin

ANNEX 2. ENCEPP CHECKLIST FOR STUDY PROTOCOLS

As attached.

ANNEX 3. ADDITIONAL INFORMATION

None.

## 4 LIST OF ABBREVIATIONS AND DEFINITION OF TERMS

ADR	Adverse Drug Reaction
AE	Adverse Event
CHA2DS2-VASc score	Congestive heart failure, Hypertension, Age ( $\geq 75$ ), Diabetes mellitus, Stroke/TIA, Vascular disease, Age 65-74, Sex category
CDMS	Clinical Data Management Systems
CRF	Case Report Form
CRO	Contract Research Organization
CrCl	Creatinine Clearance
CSR	Clinical Study Report
DM	Data Management
DVP	Data Validation Plan
GCP	Good Clinical Practice
HAS-BLED	Hypertension, Abnormal renal and liver function, Stroke (1 point), Bleeding history or predisposition, Labile INR, Elderly ( $>65$ years), Drugs and Alcohol
ICH	International Conference on Harmonization
IRB	Institutional Review Board
MedDRA	Medical Dictionary for Regulatory Activities
MG	Milligram
NVAF	Non-Valvular Atrial Fibrillation
PACT-Q ®	Perception of Anticoagulant Treatment Questionnaire
PMS	Post-Marketing Surveillance
PT	Preferred Term
SAE	Serious Adverse Event
SAP	Statistical Analysis Plan
SAS	Statistical Analysis System ®

SOC	System Organ Class
SOP	Standard Operating Procedure

DRAFT

## 5 INTRODUCTION

This Statistical Analysis Plan (SAP) is based on the final protocol 1160-0286 dated 15 March 2017 (version 1.0) and the protocol administrative memorandums that have been approved by Institutional Review Board (IRB). The SAP provides details on the planned statistical methodology for analysis of the study data, and also outlines the statistical programming specifications for the tables. It describes the safety variables, anticipated data transformations, manipulations, coding, and other details of the analyses not provided in the study protocol. A detailed description of the planned table and figures to be presented in the clinical study report (CSR) is provided in the accompanying mock-up tables documents. This SAP only covers the planned analysis of all safety and efficacy data collected on paper (source documents) and captured in case report forms (CRFs).

This SAP is written with consideration of the recommendations outlined in the International Conference on Harmonisation (ICH) E9 guideline entitled, "Guidance for Industry: Statistical Principles for Clinical Trials" and the ICH E3 guideline entitled, "Guidance for Industry: Structure and Content of Clinical Study Reports".

## 6 STUDY OBJECTIVES AND ENDPOINTS

### 6.1 Study Objectives

#### Objective 1

To describe the treatment perception from patients with non-valvular atrial fibrillation (NVAF) receiving Pradaxa® or VKA for stroke prevention by using the self-estimation questionnaire of PACT-Q during a 6-month study period.

#### Objective 2

To investigate the patient's characteristics.

Two cohorts of patients will be recruited:

#### Cohort A:

Patients who had been treated with VKA and have switched to Pradaxa®.

#### Cohort B:

Patients who are newly diagnosed with NVAF and initiated on either Pradaxa® or VKA.

### 6.2 Endpoints

#### 6.2.1 Primary Endpoint(s)

##### Cohort A (patients switched from VKA to Pradaxa®)

- Mean PACT-Q2 scores at the second (30-45 days) and the last assessment (150-210 days) compared to baseline assessment.

##### Cohort B (patients newly initiated Pradaxa® or VKA)

- Mean PACT-Q2 scores at the second (30-45 days) and the last assessment (150-210 days) compared between 2 treatment groups.

#### 6.2.2 Secondary Endpoints

##### Cohort A (patients switched from VKA to Pradaxa®)

- Mean PACT-Q2 score at the last assessment (150-210 days) compared to the second assessment (30-45 days).

##### Cohort B (patients newly initiated Pradaxa® or VKA)

- Description of mean PACT-Q1 score at baseline.

### 6.2.3 Safety Endpoints

- AEs (i.e. Pradaxa® relevant ADR (serious and non-serious), fatal AEs, and pregnancies)

Safety analyses will be performed separately for Cohort A and Cohort B.

## 7 STUDY METHOD

### 7.1 Overall Study Design and Plan

This is a non-interventional, single-country, multi-center study based on newly collected data. The study will enroll consented patients with NVAF in Taiwan with a previous VKA therapy, followed by switching to Pradaxa® (Cohort A) OR patients being newly diagnosed with NVAF and initiated on Pradaxa® or VKA (Cohort B). Patients will be followed up over an observation period of 6 months. Data will be collected at 3 time points:

1. Baseline (e.g., the enrolment date for Cohort A; the date of initiation on Pradaxa® or VKA for Cohort B).
2. 30 to 45 days after baseline (initiation period).
3. *150 to 210 days after baseline (continuation period).*

#### 7.1.1 Schedule of Assessments

This is a non-interventional, observational study, all the tests collected at baseline and subsequent visits will be performed as judged appropriate by the treating physicians, and the results of interest will be recorded only if they are available. This study does not require additional tests or examinations to be performed throughout the entire study period

However, below is the recommended data collection schedule that most likely mirrors the patterns of routine clinical care of most NVAF patients for stroke prevention. The sign "X" indicates when the data will be collected if available.

**Table 7.1 Data Collection Schedule**

Visit	1	2	3
Assessment	Baseline	Initiation period	Continuation period

Day(s) and allowed window*	1	30 to 45	150 to 210
Informed consent 	X		
Inclusion/exclusion criteria	X		
Reimbursement status 	X		
Patient demographics 	X		
Weight 	X	X	X
Concomitant diseases/comorbidities	X	X	X
Comorbidities, risk factors, and medical history related to NVAF 	X		
Concomitant therapies 	X	X	X
Concomitant therapies related to CHA 2 DS 2 -VASc and HAS-BLED 	X		
Collection of serum creatinine to calculate creatinine clearance 	X	X	X
Collection of lab data related to CHA 2 DS 2 -VASc and HAS-BLED 	X		
CHA 2 DS 2 -VASc score	X		
HAS-BLED score	X		
Duration of previous VKA treatment (Cohort A only)	X		
Reasons for switching from VKA to Pradaxa® (Cohort A only)	X		
Record Pradaxa® dosing (110 or 150mg) and reasons for dose changes if applicable	←→		
PACT-Q1 questionnaire	X (Cohort B only)		
PACT-Q2 questionnaire	X (Cohort A only)	X (both cohorts)	X (both cohorts)
Reason for Pradaxa® or VKA discontinuation	←→		
Safety reporting 	←→		

\*Only lab data assessed within the following allowed window and according to regular practice will be collected:

-Baseline: the most updated data conducted prior to enrolment

-Visit 2: within 30-45 days after baseline

-Visit 3: within 150-210 days after baseline

1. Written informed consent must be obtained prior to the baseline visit assessment.
2. Reimbursement status includes reimbursed, partially reimbursed, or private pay.
3. Age, gender, race, education level, height, weight, and BMI.
4. Weight will be recorded at each visit if possible to calculate BMI (baseline only) and creatinine clearance.
5. Comorbidities, risk factors, and medical history related to NVAF include: diabetes mellitus, hypertension, ischaemic heart disease, congestive heart failure, left ventricular dysfunction, stroke, transient ischaemic attack, thromboembolism, vascular disease (myocardial infarction, peripheral artery disease, and complex aortic plaque), abnormal renal function, abnormal liver function (e.g. cirrhosis), bleeding (e.g. prior major bleeding, predisposition to bleeding/anemia), and alcohol usage. The data prior to enrolment will be collected.
6. The current concomitant therapies within 1 month prior to enrolment will be collected. Changes in concomitant therapies will be collected at Visit 2 and Visit 3.
7. The concomitant therapies related to CHA2DS2-VASc and HAS-BLED score prior to enrolment will be collected, including chronic dialysis or renal transplant due to abnormal renal function, and medication usage predisposing to bleeding (antiplatelet agents or nonsteroidal anti-inflammatory drugs (NSAIDs)).
8. Serum creatinine assessment conducted within the allowed window of lab assessment\* will be collected to calculate CrCl according to Cockcroft-Gault formula.
9. The lab assessments include: renal function test (serum creatinine, same as the collection of CrCl at baseline described in #8), liver function tests (bilirubin, aspartate aminotransferase (AST), alanine aminotransferase (ALT), and alkaline phosphatase (AP)), and international normalized ratio (INR, including prothrombin time (PT)). Only the most updated results of assessments conducted prior to enrolment will be collected.
10. Pradaxa® relevant ADR (serious and non-serious), fatal AEs, and pregnancies.

## 7.2 Selection of Population and Inclusion/Exclusion Criteria

### 7.2.1 Inclusion Criteria

#### **Cohort A** (patients switched from VKA to Pradaxa®)

- 1.A. Written informed consent prior to participation.
- 2.A. Female or male patients  $\geq 20$  years of age with a diagnosis of non-valvular atrial fibrillation (NVAF).
- 3.A. At least 3 months of continuous VKA treatment for stroke prevention prior to baseline assessment.
- 4.A. Patients switched to Pradaxa® prior to baseline assessment according to the physician's discretion and the Summary of Product Characteristics (SmPCs)/reimbursement criteria.

OR

#### **Cohort B** (patients newly initiated Pradaxa® or VKA)

- 1.B. Written informed consent prior to participation.
- 2.B. Female or male patients  $\geq 20$  years of age, newly diagnosed with NVAF, and no previous treatment for stroke prevention (no use of any OAC within 1 year prior to enrolment).
- 3.B. Patients initiated stroke prevention treatment with Pradaxa® or VKA according to the physician's discretion and the SmPCs/reimbursement criteria.

### 7.2.2 Exclusion Criteria

1. Contraindication to the use of Pradaxa® or VKA as described in the SmPCs.
2. Patients receiving Pradaxa® or VKA for any other condition than stroke prevention in NVAF.
3. Current participation in any clinical trial of a drug or device.
4. Current participation in an AF-related registry, e.g. the Gloria AF program.

## 7.3 Randomization and Blinding

This is a non-interventional, observational, and post-marketing study. Randomization and blinding are not applicable.

## 7.4 Sample Size

It is planned that approximately 1000 patients from around 20 medical centers or regional hospitals will be recruited in the study. An estimated sub-group allocation basing on real-world practice in Taiwan includes approximately 300 patients in Cohort A (patients switched from VKA to Pradaxa®) and around 700 patients in Cohort B (patients newly initiated Pradaxa® or VKA), with about 500 patients receiving Pradaxa® and 200 patients receiving VKA. Consecutive enrolment will be performed during whole recruitment period to minimize selection bias. The actual number of patients in each cohort will be according to the patient distribution in the real-world practice.

Total number		1000	
Estimated number in sub-grouping	Cohort A —VKA switches to Pradaxa®		300
	Cohort B —Newly initiator	Pradaxa®	500
		VKA	200

## 8 GENERAL CONSIDERATIONS

### 8.1 Relevant SOPs and Policies

The data management (DM) will carry out verification procedures upon double data entry completion. Data entered in the first database has to be verified against the data entered in the second database for comparison and verification purposes. All discrepancies shall be recorded and data verification output shall be generated after this process. The data management will verify the discrepancies between first entry and second entry against the hard copy CRF. All verified data must be uploaded to the updated database(s). Data verification output and relevant records will be stored properly and securely.

To ensure the data reliability, data management will validate data based on data validation plan and reconfirm those unreliable values for all collected data includes safety and efficacy data. The locked data will be treated as the analyzable data.

Statistical Analysis Plan (SAP) will be developed from first patient enrollment. The draft SAP

will be issued based on the approved protocol, approved amendments and the CRF.

All process will follow the relevant SOPs as follow:

DM 1709	Data Entry Procedure
DM 1710	Data Verification Procedure
DM 1711	Data Validation Procedure
DM 1712	Data Clarification Procedure
DM 1713	Data Lock Procedure
DM 1719	Statistical Analysis Plan

## 8.2 Timing of Analyses

The final analysis will take place when all enrolled patients complete the study or permanently discontinued from the study. After the relevant data management processes are completed and data clean status is claimed, the database will be locked. The final analysis will be conducted based on the lock data.

## 8.3 Analysis Populations

In this study, there will be two populations, Full Analysis Set (FAS), and Safety population set up for analysis. The populations for analysis applied into this study are defined as following:

### Full Analysis Set (FAS)

All eligible patients.

### Safety Population

All enrolled patients with an actual follow-up.

## 8.4 Covariates and Subgroups

Demographic and clinical characteristics, including age, gender, BMI classification (BMI<18.5, 18.5≤BMI<24, 24≤BMI<27, BMI≥27), CHA2DS2-VASc score, HAS-BLED score, kidney function (creatinine clearance), stroke and/or bleeding related risk factors, will be

considered as covariates/predictors for conducting propensity score matching the two subgroups in cohort B.

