According to the previous study results, the decision in clinical practice to use Pradaxa® or established vitamin K antagonists (VKAs) depends on many factors related to: (a) The patient: health status, comorbid and demographic conditions, perception of anticoagulant treatment, understanding of the burden of the disease, access to the medication, educational measures informing about medications, and reimbursement status. (b) The treating physician: stroke risk assessment, bleeding risk assessment, adherence to guidelines, access and use of medical education, and overall local health care system. These factors in the real-world clinical practice vary in countries with different health care systems; patients who newly start anticoagulation treatment versus those have had anticoagulation experience already; and the initiation versus the mid-term follow-up on Pradaxa®. According to National Health Insurance (NHI) in Taiwan, Pradaxa® is prescribed to a newly diagnosed NVAF patient with stroke or systemic embolism, left ventricular ejection fraction < 40%, symptomatic heart failure (New York Heart Association Class ≥ 2), age ≥ 75 years, or age ≥ 65 years with one of the following risk factors: diabetes mellitus, coronary artery disease (CAD), or hypertension. Pradaxa® should not be considered if the patient has valvular heart disease, stroke within 14 days, serious stroke within 6 months, the risk of increasing ischemia, creatinine clearance (CrCl) < 30 mL/min, active liver disease, or pregnant.

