9.3.3 Covariates

Demographic and clinical characteristics, including age, gender, body weight, CHA2DS2-VASc score, HAS-BLED score, kidney function (creatinine clearance), stroke and/or bleeding related risk factors, co-morbidities, and/or concomitant therapies will be collected if available. If any covariates or confounding/interacting variables that may be possibly predictive of the outcome under study are noted, additional analyses may be carried out to identify its effect. Details of handling covariates will be given in the statistical analysis plan (SAP), if any covariates of interest are detected.

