9.3.4 Baseline characteristics and general information

Baseline characteristics of patients include:

- Demographics: Age, gender, race, education level, height, weight, and BMI
- Comorbidities
- Concomitant therapies
- Stroke- and/or bleeding related risk factors in the medical history
- CHA₂DS₂-VASc score
- HAS-BLED score
- Kidney function (creatinine clearance)
- Dosing of Pradaxa® and the reasons for dose change
- Duration of previous VKA treatment (for Cohort A only)

For the following 6 sections, data collection detail is described in Section 9.2.3.

1. Concomitant diseases/comorbidities

All the concomitant diseases/comorbidities in the medical history will be collected at Baseline visit (Visit 1). Newly occurred or changed concomitant diseases/comorbidities compared with the previous visit will be collected at the initiation period (Visit 2) and the continuation period (Visit 3).

2. Comorbidities/Risk factors/Medical history related to NVAF⁸

For the comorbidities/risk factors/medical history related to NVAF, the status (active/past or never occurred, no retrospective time limit is set) should be documented at enrolment, if available. The comorbidities/risk factors/medical history related to NVAF include diabetes mellitus, hypertension, ischaemic heart disease, heart failure, stroke, transient ischaemic attack, and thromboembolism.

3. Concomitant therapies

Current concomitant therapies within 1 month prior to enrolment will be collected. Changes in concomitant therapies compared with the previous visit will be collected at the initiation period (Visit 2) and the continuation period (Visit 3). Data of interest include start/stop date or ongoing, dose, unit, and frequency.

For the concomitant therapy as an element for the CHA₂DS₂-VASc score or HAS-BLED score calculation, including chronic dialysis or renal transplant due to abnormal renal function and medication usage predisposing to bleeding (antiplatelet agents or nonsteroidal anti-inflammatory drugs (NSAIDs)), information will only be collected as active/past or never occurred prior to enrolment (no retrospective time limit is set).

4. Calculation of CHA₂DS₂-VASc score⁹

The CHA₂DS₂-VASc score is a clinical prediction rule for estimating the risk of stroke in patients with non-rheumatic AF. The CHA₂DS₂-VASc score is composed of 8 items with a maximum score of 9. Among all the items, 2 of them have extra weight with 2 points,

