including "age 75 and above" and "stroke, transient ischemic attack, and thromboembolism", while the other 6 items are counted as 1 point of each. A higher score corresponds to a greater risk of stroke. The available information for verifying the items in CHA₂DS₂-VASc score will be collected from source data and will be recorded on the CRFs. The CHA₂DS₂-VASc score will be calculated according to **Table 2**.

Table 2 The 2009 Birmingham Schema Expressed as a Point-Based Scoring System, With the Acronym CHA₂DS₂-VASc

Letter	Clinical Characteristic	Score
C	Congestive heart failure or left ventricular dysfunction	1
H	Hypertension	1
A₂	Age \geq 75 years	2
D	Diabetes Mellitus	1
S₂	Previous stroke, transient ischemic attack, or thromboembolism	2
V	Vascular disease (prior myocardial infarction, peripheral artery disease, or aortic plaque)	1
A	Age 65–74 years	1
Sc	Sex category (i.e. female sex)	1

5. Calculation of HAS-BLED score¹⁰

HAS-BLED is a scoring system developed to assess 1-year risk of major bleeding in patients with AF. The HAS-BLED score is composed of 7 items with a maximum score of 9. Among all the items, 2 of them will be scored with 1 or 2 points depending on the number of corresponded description, including "abnormal renal and liver function" and "drugs or alcohol", while the other 5 items are counted as 1 point of each. A higher score corresponds to a greater risk of bleeding, and a score of \geq 3 points indicates "high risk". The available information for verifying the items in HAS-BLED score will be collected from source data and will be recorded on the CRFs. The HAS-BLED score will be calculated according to **Table 3**.

Table 3 Clinical Characteristics Composing the HAS-BLED Bleeding Risk Score

Letter	Clinical Characteristic	Score
H	Hypertension ¹	1
A	Abnormal renal function ² and abnormal liver function ³ (1 point each)	1 or 2
S	Stroke ⁴	1
B	Bleeding ⁵	1
L	Labile INRs ⁶	1
E	Elderly, age $>$ 65 years	1

D	Drugs or alcohol (1 point each) ⁷	1 or 2

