
1. Hypertension should be uncontrolled, with systolic blood pressure > 160 mmHg.
 
2. Abnormal kidney function is classified as a presence of chronic dialysis, renal transplantation, or serum creatinine $\geq 200 \mu\text{mol/L}$.
 
3. Abnormal liver function is defined as the chronic hepatic disease (e.g., cirrhosis) or biochemical evidence of significant hepatic derangement (e.g., bilirubin $> 2 \times$ upper limit of normal, in association with AST/ALT/AP $> 3 \times$ upper limit normal, and so forth.)
 
4. Previous history, particularly lacunar.
 
5. Bleeding history, such as prior major bleeding or predisposition to bleeding (e.g., anemia).
 
6. Labile international normalized ratio (INR, e.g., therapeutic time in range $< 60\%$).
 
7. Drugs are medication usage predisposing to bleeding (e.g. antiplatelet agents or NSAIDs).
 
Ethanol abuse is classified as ≥ 8 units of alcoholic consumption per week.
		

6. Calculation of creatinine clearance (CrCl)

Kidney function will be evaluated according to creatinine clearance (CrCl). Serum creatinine available from medical chart and weight assessed according to the visit schedule will be collected to calculate the CrCl value by Cockcroft-Gault formula*. In addition, only serum creatinine data assessed within the allowed window will be collected. The allowed window at each visit is listed as below:

- Baseline: the most updated data assessed prior to enrolment
- Visit 2 (initiation period): within 30-45 days after baseline
- Visit 3 (continuation period): within 150-210 days after baseline

*Cockcroft-Gault formula:

If the information of serum creatinine and weight are both collected and recorded on the CRFs, the CrCl will be calculated via Cockcroft-Gault formula which could be measured in different serum creatinine units (mg/dL or $\mu\text{mol/L}$).^{11,12}

- When serum creatinine is measured in mg/dL:

The resulting value is multiplied by a constant of 0.85 if the patient is female.

$$eC_{Cr} = \frac{(140 - \text{Age}) \times \text{Mass (in kilograms)} \times [0.85 \text{ if Female}]}{72 \times \text{Serum Creatinine (in mg/dL)}}$$

- When serum creatinine is measured in $\mu\text{mol/L}$:

Constant is 1.23 for male and 1.04 for female.

$$eC_{Cr} = \frac{(140 - \text{Age}) \times \text{Mass (in kilograms)} \times \text{Constant}}{\text{Serum Creatinine (in } \mu\text{mol/L)}}$$

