9.7.1 Main analysis

Baseline demographic and clinical characteristics

Descriptive summary will be presented for baseline demographic and clinical characteristics of all patients enrolled in Cohort A, Cohort B Pradaxa® initiators, and Cohort B VKA initiators, respectively. For continuous variables, number of patients, mean, standard deviation (SD), median, Q1 (lower quartile), Q3 (upper quartile), minimum, and maximum will be presented. For categorical variables, frequency and percentage will be presented for each category.

Primary outcomes

For Cohort A, descriptive summary will be presented for PACT-Q2 score at baseline visit (Visit 1), Visit 2, and Visit 3 using measure of central tendency and variation (mean \pm SD, or median with inter-quartile range (IQR)). The PACT-Q2 score at Visit 2 and Visit 3 will be compared with the PACT-Q2 score at baseline visit, respectively, using paired t-test or Wilcoxon signed-rank test based on the distribution of the data.

For Cohort B, the patients newly initiated Pradaxa® or VKA will be matched with a ratio of 1:1 based on the propensity score. The covariates age, gender, body weight, CHA₂DS₂-VASC score, HAS-BLED score, kidney function (creatinine clearance), stroke and/or bleeding related risk factors, co-morbidities, and/or concomitant therapies, **if available**, will be included in the propensity score model. Details of the propensity score model and the matching procedure, such as the choice of algorithm and caliper width will be specified in the SAP. Descriptive summary of the baseline characteristics will be presented for and compared between the matched patients to check the balance of baseline characteristics between the two groups of Cohort B after propensity score matching. Moreover, standardized difference will be calculated as a measure of the balance of baseline characteristics after propensity score matching. Analyses of PACT-Q2 score will be performed on propensity score matched Pradaxa® initiators and VKA initiators. Descriptive summary will be presented for PACT-Q2 score at Visit 2 and Visit 3 using mean \pm SD, or median with IQR. PACT-Q2 score will be compared between matched Pradaxa® initiators and VKA initiators using paired t-test or Wilcoxon signed-rank test.

Secondary outcomes

For Cohort A, the PACT-Q2 score at Visit 2 and Visit 3 will be compared using paired t-test or Wilcoxon signed-rank test based on the distribution of the data.

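### The SAP's Cohort B propensity model leaves out the protocol's co-morbidity and concomitant-therapy terms and replaces body weight with BMI class, yet SAP 12 declares no differences

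*SAP*

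**What the plan says.** Protocol 9.3.3 lists the covariates to be collected: age, then "gender, body weight, CHA2DS2-VASc score, HAS-BLED score, kidney function (creatinine clearance), stroke and/or bleeding related risk factors, co-morbidities, and/or concomitant therapies". Protocol 9.7.1 repeats the list and says that these covariates, if available, will go into the propensity score model; its closing terms are "stroke and/or bleeding related risk factors, co-morbidities, and/or concomitant therapies". It leaves details of the model and the matching to the SAP, with algorithm and caliper width as examples. It adds that a "standardized difference will be calculated as a measure of the balance of baseline characteristics after propensity score matching".

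SAP 8.4 follows the same order: age, gender, a four-level BMI class, CHA2DS2-VASc, then "HAS-BLED score, kidney function (creatinine clearance), stroke and/or bleeding related risk factors, will be" used as predictors for matching. Body weight is not listed, and neither are co-morbidities or concomitant therapies. SAP 8.7 says that baseline characteristics will be compared after matching but names no measure. SAP 11.3 gives the 1:1 matching steps and a caliper of 0.001, and also names no balance measure. SAP 12 states that the SAP follows the protocol without changes or differences.

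**The concern.** The Pradaxa–VKA difference in PACT-Q2 is a primary comparison between groups that were not randomised, and matching is the only confounding control in the SAP. Protocol 9.9 names both covariate adjustment and matching as the defence against channeling. A covariate that influences drug choice but is missing from the score can stay unbalanced after matching.

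The covariate list also differs from the protocol's without any record. A reader of SAP 12 would take the protocol's model to be the one that is run.

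**Working it through.** The documents give no figure on this point, so the check is a comparison of text.

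**Step 1. The lists side by side.**

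| Protocol 9.7.1 | SAP 8.4 |
|---|---|
| Age, gender | Same |
| Body weight | BMI in four classes |
| CHA2DS2-VASc, HAS-BLED, creatinine clearance | Same |
| Stroke/bleeding risk factors | Same, not itemised in either document |
| Co-morbidities and/or concomitant therapies | Not listed |
| Standardized difference after matching | No measure named (SAP 8.7, 11.3) |

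**Step 2. How much of the omitted co-morbidity content the scores carry.** The NVAF-related co-morbidities in Protocol 9.3.4 "include diabetes mellitus, hypertension, ischaemic heart disease, heart failure, stroke, transient ischaemic attack, and thromboembolism". Against Protocol Table 2:
- diabetes: D
- hypertension: H
- heart failure: C
- stroke, transient ischaemic attack and thromboembolism: S2
- ischaemic heart disease: no item of its own

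So 6 of 7 score. The nearest item is "Vascular disease (prior myocardial infarction, peripheral artery disease, or aortic plaque", which counts coronary disease only after a myocardial infarction. The longer list in Table 1, footnote 5 (SAP Table 7.1, footnote 5) gives the same answer. Of its 13 items, 12 appear in CHA2DS2-VASc or HAS-BLED, and ischaemic heart disease is again the exception.

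**Step 3. Why that item may matter.** Protocol 7 lists the National Health Insurance criteria for Pradaxa, among them age 65 or over "with one of the following risk factors: diabetes mellitus, coronary artery disease (CAD), or hypertension". Take two men over 65 and under 75, of the same age, BMI class and creatinine clearance. Neither has another item in either score, and one has coronary disease without prior infarction. CHA2DS2-VASc = 1 (age) for both, and HAS-BLED = 1 (age) for both. The first meets the criterion and the second does not. Unless the un-itemised risk factors include ischaemic heart disease, every covariate named in SAP 8.4 is equal for these two men.

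**Step 4. Antiplatelet/NSAID use.** By name it enters only as the one-point drug item of HAS-BLED (Table 3). A total of 2 can be age plus antiplatelet use or age plus a bleeding history, and the total does not tell them apart.

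**Step 5. Body weight.** Protocol 9.3.4 computes clearance "If the information of serum creatinine and weight are both collected and recorded on the CRFs". At a given age and sex, Cockcroft-Gault fixes only weight divided by creatinine, so it recovers weight in part. Within BMI 18.5 to <24 at one height, weight can vary by 24/18.5 = 1.30-fold. The documents show no link from weight to PACT-Q2, so this ratio has no demonstrated consequence.

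**Step 6. Why the balance measure should be restated.** The SAP does not say that balance will be judged by p-values. If it were (assumption: continuous covariate with SD 1, two-sample approximation, two-sided 0.05), 200 planned VKA patients allow at most 200 pairs. An observed standardized difference below 1.96 × √(2/200) = 0.196 would be non-significant. The power to flag a true difference of 0.10 would be 16.9%, and of 0.20 it would be 51.6%. With 100 pairs the limit is 0.277, and the power is 10.5% and 29.3%.

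**The case against.** The case for leaving the SAP as it is has several parts.

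- **Delegation.** The protocol qualifies its list with and/or and if available, and leaves model details to the SAP. This holds for the coding of body size: BMI is derived from weight, and choosing classes is a modelling choice. It holds less well for whole terms. The covariates are named in the sentence before the delegation, and no SAP section gives unavailability as the reason for leaving them out.
- **Open wording.** SAP 8.4 introduces its list with including, so it is not strictly closed. But nothing else in the SAP adds the missing terms.
- **Coverage by the risk factors.** The un-itemised stroke and bleeding risk factors could take in ischaemic heart disease, which the schedule places under a heading that includes risk factors. They could also take in antiplatelet/NSAID use, which the protocol describes as predisposing to bleeding. This stands, and it is why the point is that neither item is clearly identified. Against it, the protocol lists co-morbidities and therapies as separate terms.
- **Narrow channel.** Coronary disease decides insurance eligibility only below age 75, in patients without diabetes, hypertension, prior stroke or embolism, low ejection fraction or symptomatic heart failure. This also stands and limits the likely effect.
- **Standardized difference.** SAP 5 bases the SAP on the protocol, so the protocol's measure still applies, and it may appear in the mock-up tables, which are not among the documents. This stands.

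**Conclusion.** The discrepancy is real and undeclared. SAP 8.4 departs from Protocol 9.7.1 on body size, co-morbidities and concomitant therapies, and SAP 12 says that nothing differs. Most of the omitted content enters indirectly. What remains is one co-morbidity that the named covariates do not clearly identify and that the protocol itself ties to access to Pradaxa, and one therapy item present by name only inside a sum score. This should be corrected while the SAP is still marked as a draft.

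A reader might infer more, and the documents do not support it:
- *That the Cohort B comparison is biased, or biased in a known direction.* Neither size nor direction can be derived.
- *That BMI class in place of weight damages the comparison.* No consequence is shown. The issue is the missing record.
- *That the SAP has abolished the standardized difference.* The SAP is silent on it, and the protocol's statement stands.

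A count of planned patients per model term would not be informative either, because the risk factors are not itemised. The conclusion assumes that the items in Protocol 9.3.4 and Table 1, footnote 5, are the co-morbidities meant in 9.7.1. If all recorded concomitant diseases are meant, the omission is wider.

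**What to change.** - **SAP 8.4:** itemise the stroke and bleeding risk factors, and add ischaemic heart disease and antiplatelet/NSAID use, each by recorded status, to the propensity model.
- **SAP 11.3:** restate the protocol's standardized difference as the balance measure after matching.
- **SAP 8.4 or 12:** either restore body weight, or keep BMI class and record and justify it in SAP 12. Record any other departure there too, including any co-morbidities left out because SAP 9.4 plans no coding of medical history.
- **Optional:** a covariate-adjusted comparison, supportive only. The paired test stays primary.

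**Cost.** The change is SAP wording. Both added items are already collected (SAP Table 7.1, footnotes 5 and 7), and SAP 9.3 already plans counts and percentages for these fields, so they need no new data and no coding. Restoring weight loses no further patients, because BMI and creatinine clearance already need it.

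There is a price. Status is recorded only if available, SAP 8.5 rules out imputation for efficacy and safety variables, and no other section provides for imputing covariates. Patients with missing status may therefore drop out of the score. A changed score may also lose some matches under the 0.001 caliper. The SAP should state how missing status is handled, and the number of patients lost for each reason should be reported.
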